16.2 Appendix 2: Liver event and laboratory trigger definitions & follow-up requirements

Table 16-3 Liver event and laboratory trigger definitions

Definition/ threshold	
Liver laboratory triggers	
 ALT or AST > 5 x ULN
If ALT, AST and total bilirubin normal at baseline:	
 ALP > 2 x ULN (in the absence of known bone pathology) Total bilirubin > 3 x ULN (in the absence of known Gilbert syndrome) ALT or AST > 3 x ULN and INR > 1.5 Potential Hy's Law cases (defined as ALT or AST > 3 x ULN and Total bilirubin > 2 x ULN [mainly conjugated fraction] without notable increase in ALP to > 2 x ULN) Any clinical event of jaundice (or equivalent term) ALT or AST > 3 x ULN accompanied by (general) malaise, fatigue, abdominal pain, nausea, or vomiting, or rash with eosinophilia Any adverse event potentially indicative of a liver toxicity*
If ALT or AST abnormal at baseline:	
 ALT or AST > 2x baseline or > 300 U/L (whichever occurs first)

*These events cover the following: hepatic failure, fibrosis and cirrhosis, and other liver damage-related conditions; non-infectious hepatitis; benign, malignant and unspecified liver neoplasms ULN: upper limit of normal

Table 16-4 Follow up requirements for liver laboratory triggers with liver symptoms

ALT or AST	TBL	Liver Symptoms	Action
ALT or AST increase without bilirubin increase:			
If normal at baseline: ALT or AST > 3 x ULN	Normal For patients with Gilbert's syndrome:	None	
 No change to study treatment Measure ALT, AST, ALP, GGT, TBL, direct and indirect bilirubin, PT/INR, albumin, CK, and GLDH in 48-72 hours. Follow-up for symptoms.
If elevated at baseline: ALT or AST > 2 x baseline or > 300 U/L (whichever occurs first)	No change in baseline TBL		
ALT or AST increase with bilirubin increase:			
If normal at baseline: ALT or AST > 5 x ULN for more than two weeks	Normal For patients with Gilbert's syndrome:	None	
 Interrupt study drug Measure ALT, AST, ALP, GGT, TBL, direct and indirect bilirubin, PT/INR, albumin, CK, and GLDH in 48-72 hours. Follow-up for symptoms. Initiate close monitoring and workup for competing etiologies.
If elevated at baseline: ALT or AST > 3 x baseline or > 300 U/L (whichever occurs first) for more than two weeks	No change in baseline TBL		
If normal at baseline: ALT or AST > 8 x ULN	Normal	None	
 Study drug can be restarted only if another etiology is identified and liver enzymes return to baseline.
ALT or AST increase with bilirubin increase:			
If normal at baseline: ALT or AST > 3 x ULN	TBL > 2 x ULN (or INR > 1.5)	None	
If elevated at baseline: ALT or AST > 2 x baseline or > 300 U/L (whichever occurs first)	For patients with Gilbert's syndrome: Doubling of direct bilirubin		
If normal at baseline: ALT or AST > 3 x ULN	Normal or elevated		

ALT or AST	TBL	Liver Symptoms	Action
If elevated at baseline: ALT or AST > 2 x baseline or > 300 U/L (whichever occurs first)		Severe fatigue, nausea, vomiting, right upper quadrant pain	

Table 16-5 Follow up requirements for liver laboratory triggers

[figure not shown]
Criteria	Actions required	Follow-up monitoring
Total Bilirubin (isolated)		
>1.5 – 3.0 ULN	
 Maintain treatment Repeat LFTs within 48-72 hours 	Monitor LFTs weekly until resolution ^a to ≤ Grade 1 or to baseline
> 3 - 10 × ULN (in the absence of known Gilbert syndrome)	
 Interrupt treatment Repeat LFT within 48-72 hours Hospitalize if clinically appropriate Establish causality Record the AE and contributing factors (e.g. conmeds, med hx, lab) in the appropriate CRF 	Monitor LFTs weekly until resolution ^a to ≤ Grade 1 or to baseline (ALT, AST, total bilirubin, Alb, PT/INR, ALP and GGT) Test for hemolysis (e.g. reticulocytes, haptoglobin, unconjugated [indirect] bilirubin)
> 10 x ULN	
 Discontinue the study treatment immediately Hospitalize the participant Establish causality Record the AE and contributing factors(e.g. conmeds, med hx, lab)in the appropriate CRF 	ALT, AST, total bilirubin, Alb, PT/INR, ALP and GGT until resolution ^c (frequency at investigator discretion)
Any AE potentially indicative of a liver toxicity*	
 Consider study treatment interruption or discontinuation Hospitalization if clinically appropriate Establish causality Record the AE and contributing factors(e.g., conmeds, med hx, lab)in the appropriate CRF 	Investigator discretion

^aResolution is defined as an outcome of one of the following: (1) return to baseline values, (2) stable values at three subsequent monitoring visits at least 2 weeks apart, (3) remain at elevated level after a maximum of 6 months, (4) liver transplantation, and (5) death.

Based on investigator's discretion investigation(s) for contributing factors for the liver event can include: Serology tests, imaging and pathology assessments, hepatologist's consultancy; obtaining more detailed history of symptoms and prior or concurrent diseases, history of concomitant drug use, exclusion of underlying liver disease.

16.3 Appendix 3: Flowchart Using the Suita Score to Establish LDL-C Management Targets, from the Perspective of CAD Prevention (JAS 2017 guideline)

Figure 16-1 Flowchart Using the Suita Score to Establish LDL-C Management Targets, from the Perspective of CAD Prevention

- The Suita score is calculated based on [Figure 16-2](#).
- Note: For patients diagnosed with FH and those diagnosed with familial type III hyperlipidemia, do not use this chart.

Figure 16-2 Model for Predicting CAD Onset Using the Saita Score

	Range	Score
1. Age	35-44	30
	45-54	38
	55-64	45
	65-69	51
	70+	53
2. Gender	Men	0
	Women	-7
3. Smoking*	Yes	5
4. Blood pressure**	SBP <120 and DBP <80	-7
	SBP =120-139 and/or DBP=80-89	0
	SBP =140-159 and/or DBP=90-99	4
	SBP ≥ 160 and/or DBP ≥ 100	6
5. HDL-C	<40	0
	40-59	-5
	≥ 60	-6
6. LDL-C	< 100	0
	100-139	5
	140-159	7
	160-179	10
	≥ 180	11
7. Impaired glucose tolerance	Yes	5
8. Family history of premature CAD	Yes	5

Total score of 1-8	Probability of CAD within the next 10 years (%)	Probability range (%)		Median of probability (%)	Category
		Minimum	Maximum		
≤ 35	< 1	1.0	0.5	Low risk	
36-40	1	1.3	1.9	1.6	
41-45	2	2.1	3.1	2.6	Moderate risk
46-50	3	3.4	5.0	4.2	
51-55	5	5.0	8.1	6.6	
56-60	9	8.9	13.0	11.0	
61-65	14	14.0	20.6	17.3	
66-70	22	22.4	26.7	24.6	
≥ 71	>28	28.1		≥ 28.1	High risk

*Ex-smokers should be regarded as nonsmokers. Note that the risk of CAD decreases by almost half 1 year after smoking cessation and drops to the same level as in nonsmokers after 15 years of smoking cessation.

**The current values are used even if the patient is currently undergoing treatment or not. However, counsel the patient while keeping in mind that patients undergoing treatment for hypertension have a higher risk of CAD than those who have the same blood pressure value without undergoing treatment.

Note: The advantages and dis-advantages of lipid management in patients aged < 40 years of age are at the discretion of the attending physician; however, if lipid management is to be carried out, then the Saita score absolute risk for 35-44 years of age group is used.

Source: JAS 2017 guideline ([Kinoshita et al 2018](#))

16.4 Appendix 4: Diagnostic Criteria for Heterozygous FH in adults (15 years of age or older)

Table 16-6 Diagnostic criteria for heterozygous FH in adults (15 years of age or older)

- Hyper-LDL-cholesterolemia (an untreated LDL-C level ≥ 180 mg/dL)
- Tendon xanthomas (thickening of tendons on dorsal side of the hands, elbows, knees or Achilles tendon hypertrophy) or xanthoma tuberosum
- Family history of FH or premature CAD (within the patient's second-degree relatives)
- The diagnosis should be made after excluding secondary dyslipidemia.
- If a patient meets two or more of the above-mentioned criteria, the condition should be diagnosed as FH. In case of suspected heterozygous FH, making a diagnosis using genetic testing is desirable.
- Xanthelasma is not included in xanthoma tuberosum.
- Achilles tendon hypertrophy is diagnosed if the Achilles tendon thickness is ≥ 9 mm on X-ray imaging.

- An LDL-C level of ≥ 250 mg/dL strongly suggests FH.
- If a patient is already receiving drug therapy, the lipid level that led to treatment should be used as the reference for diagnosis.
- Premature CAD is defined as the occurrence of CAD in men < 55 years of age or women < 65 years of age, respectively.
- If FH is diagnosed, it is preferable to also examine the patient's family members.
- These diagnostic criteria also apply to HoFH.

Source: *JAS 2017 guideline (Kinoshita et al 2018)*

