6.5.1 Dose modifications

Study drug administration should be temporarily interrupted or permanently discontinued in participants with:

1. Intolerable AEs, or if the investigator believes that continuing dosing will be detrimental to the participant's mental or physical health. This includes severe or serious reactions at the injection site and any anaphylactic type reactions.
2. Liver laboratory values meeting the study drug interruption criteria listed in [Table 16-4](#) and [Table 16-5](#).
3. Unexplained creatine kinase (CK) values $>5 \times$ ULN confirmed by repeat test when the CK elevation is associated with muscle pain, muscle tenderness and/or muscle weakness, or new onset renal dysfunction.

Study treatment may be restarted at the discretion of the investigator, if the reason for discontinuation has resolved.

The dose interruptions must be recorded on an appropriate eCRF.

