8.4.1 Laboratory evaluations

Specimens will be obtained at the time points in the Assessment Schedule ([Table 8-1](#)).

Central laboratory will be used for analysis of all specimens collected, with the exception of urine pregnancy tests and urine dipstick tests, which will be done locally (using testing materials supplied by the central laboratory). Serum pregnancy tests at screening will be done by the central laboratory. Details on the collections, shipment of samples and reporting of results by the central laboratory are provided to investigators in a Laboratory Manual.

Note: Efficacy laboratory assessments (e.g., LDL-C and PCSK9) are described in [Section 8.3](#).

Clinically significant abnormalities must be recorded as either medical history/current medical conditions or adverse events as appropriate.

Clinically notable laboratory findings are defined in [Section 16.1](#).

Table 8-3 Clinical Laboratory Assessments

Test Category	Test Name
Hematology	Hematocrit, Hemoglobin, Mean cell hemoglobin (MCH), Mean corpuscular hemoglobin concentration (MCHC), MCV, Platelets, Red blood cells (RBC), White blood cells (WBC), Differential (% of Basophils, Eosinophils, Lymphocytes, Monocytes, Neutrophils)

Test Category	Test Name
Chemistry	Albumin, Alkaline phosphatase, ALT, AST, GGT, Calcium, Magnesium, Phosphorus, Chloride, Sodium, Potassium, Creatinine, CK, Direct Bilirubin, total Bilirubin (TBL), Blood Urea Nitrogen (BUN), Uric Acid, Lactate Dehydrogenase (LDH), Hemoglobin A1c (HbA1c) ^c , eGFR ^{c, d}
Inflammatory marker	High sensitivity C-reactive protein (hsCRP) (fasting) [REDACTED]
Cytokines	IL-6, IFN- γ , TNF- α
Urinalysis ^a	Macroscopic Panel (Dipstick): Bilirubin, Blood, Glucose, Ketones, Leukocytes esterase, Nitrite, pH, Protein, Urobilinogen, Specific Gravity, urine sediment (microscopic examination will be only performed in the event of abnormalities)
Coagulation ^b	PT, INR, Activated partial thromboplastin time (APTT)
Steroid hormones ^e	Aldosterone, Cortisol, Estradiol ^f , Progesterone ^f , Testosterone ^g
Pregnancy Test	Serum / Urine pregnancy test (see Section 8.4.3)
Other	Fasting Plasma Glucose Tryptase (only in case of anaphylaxis)

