10.2 Additional Safety Monitoring

10.2.1 Liver safety monitoring

To ensure participant safety and enhance reliability in determining the hepatotoxic potential of an investigational drug, a standardized process for identification, monitoring and evaluation of liver events has to be followed.

Please refer to [Table 16-3](#) in Appendix 2 for complete definitions of liver laboratory triggers.

Once a participant is exposed to study treatment, every liver event defined in [Table 16-3](#) should be followed up by the investigator or designated personnel at the trial site, as summarized below. Additional details on actions required in case of liver events are outlined in [Table 16-4](#). Repeat liver chemistry tests (i.e. ALT, AST, TBL, PT/INR, ALP and GGT) to confirm elevation.

- These liver chemistry repeats will be performed using the central laboratory. If results will not be available from the central laboratory, then the repeats can also be performed at a local laboratory to monitor the safety of the participant. If a liver event is subsequently reported, any local liver chemistry tests previously conducted that are associated with this event should have results recorded on the appropriate eCRF.
- If the initial elevation is confirmed, close observation of the participant will be initiated, including consideration of treatment interruption if deemed appropriate.
- Discontinuation of the investigational drug (refer to the Discontinuation of study treatment section), if appropriate
- Hospitalization of the participant if appropriate
- Causality assessment of the liver event
- Thorough follow-up of the liver event should include
 - These investigations can include based on investigator's discretion: serology tests, imaging and pathology assessments, hepatologist's consultancy; obtaining more detailed history of symptoms and prior or concurrent diseases, history of concomitant drug use, exclusion of underlying liver disease

All follow-up information and procedures performed must be recorded as appropriate in the eCRF.

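### The symptomatic row of Table 16-4 omits rash with eosinophilia, a liver event in Table 16-3, so dosing continues or is left to discretion where nausea would require a stop

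*Protocol*

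**What the plan says.** Table 16-3 in Protocol Appendix 2 (Section 16.2) defines liver events. For participants whose ALT, AST and total bilirubin are normal at baseline, one entry reads "ALT or AST > 3 x ULN accompanied by (general) malaise, fatigue, abdominal pain, nausea, or vomiting, or rash with eosinophilia". Section 10.2.1 asks for follow-up of every Table 16-3 event and refers to Table 16-4 for the actions required.

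Table 16-4 has a column for liver symptoms. One row fills it with "Severe fatigue, nausea, vomiting, right upper quadrant pain", at ALT or AST above 3 x ULN (normal baseline) and bilirubin normal or elevated. Every other row has 'None' in that column. The rows after the first carry an interruption instruction and this condition: "Study drug can be restarted only if another etiology is identified and liver enzymes return to baseline".

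The general rules are looser:

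- Section 10.2.1: "If the initial elevation is confirmed, close observation of the participant will be initiated, including consideration of treatment interruption if deemed appropriate". It also lists "Causality assessment of the liver event".
- Section 6.5.1 item 2 calls for temporary interruption or permanent discontinuation for "Liver laboratory values meeting the study drug interruption criteria listed in" Tables 16-4 and 16-5.
- Section 6.5.1, after any interruption: "Study treatment may be restarted at the discretion of the investigator, if the reason for discontinuation has resolved".

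**The concern.** Table 16-3 puts rash with eosinophilia in the same entry, at the same enzyme threshold, as nausea and vomiting. Table 16-4 carries nausea and vomiting forward to an action and does not carry rash with eosinophilia forward. Two participants with the same enzymes, both with a protocol-defined liver event, can therefore face different rules on the next injection, and the protocol gives no reason for the difference.

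The stake is mainly re-dosing. The injections are months apart, so an enzyme rise can settle before the next one is due. Rash with eosinophilia alongside raised transaminases is a hypersensitivity-type picture, and re-exposure with no other cause identified is the situation that the restart condition in Table 16-4 is meant to prevent.

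**Working it through.** The plan states no figure on this point, so the check is a row-by-row match followed by simple dose arithmetic.

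**Test case.** Normal baseline tests; ALT 4 x ULN on study; bilirubin normal; INR not above 1.5.

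| Rule | With nausea | With rash with eosinophilia only |
|---|---|---|
| Table 16-3 | Liver event | Liver event |
| Table 16-4, symptomatic row | Applies: interrupt, restart restricted | Not listed |
| Table 16-4, first row (symptoms 'None') | Does not apply | Applies if rash is not counted as a liver symptom: treatment continues, liver panel in 48-72 hours, symptom follow-up |
| Section 6.5.2.1 (DILI) | Needs a bilirubin rise; not met | Needs a bilirubin rise; not met |
| Table 16-5, row for AEs suggesting liver toxicity | Interruption or discontinuation only to be considered | The same, if the event is judged to be such an AE; the Table 16-3 footnote describing these AEs does not mention rash |
| Section 10.2.1 | Superseded by the specific row | Interruption to be considered |
| Section 6.5.1, restart | Superseded by the restart condition in Table 16-4 | Investigator discretion |

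**Two readings of the rash case.**

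1. Rash is not a liver symptom, so the rows marked 'None' apply. Treatment then continues at more than 3 and up to 5 x ULN for any duration, and at more than 5 and up to 8 x ULN for up to two weeks. Beyond that (above 5 x ULN for more than two weeks, or above 8 x ULN) Table 16-4 interrupts drug even without symptoms.
2. Rash is a symptom, so the 'None' rows do not apply and neither does the symptomatic row. Sections 10.2.1 and 6.5.1 then govern by discretion. The enzyme ceiling from reading 1 cannot be used here, because it comes from 'None' rows.

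Neither reading gives the event the rule that nausea receives.

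**Dose arithmetic** (dosing days from Protocol Section 3). Day 1 to Day 90: 90 - 1 = 89 days. Day 90 to Day 270: 270 - 90 = 180 days. Injections that a post-dose event can affect: 3 - 1 = 2 (Day 90 and Day 270). Injections before the Day 180 endpoint: 2 (Day 1 and Day 90).

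**The case against.** The strongest reply is that Table 16-3 lists triggers, Table 16-4 lists actions, and the two need not match item for item. ALP above 2 x ULN, for example, is a trigger with no Table 16-4 row. 'Severe' fatigue and 'right upper quadrant' pain look like deliberate grading of the Table 16-3 terms. That stands, and it is why malaise, milder fatigue and other abdominal pain are not treated here as omissions. It does not account for rash with eosinophilia, which appears in no form, graded or otherwise.

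A reader might infer that the protocol has no rule at all for this event. The documents do not support that. The first row of Table 16-4 can be read to cover it, Section 10.2.1 requires follow-up with causality assessment, and Table 16-5 may apply. Section 6.5.1 item 1 covers dosing that the investigator believes would be detrimental. Section 9.1.1 requires treatment to stop where participation might put the participant at risk, and a DMC reviews safety data (Section 10.2.3). These backstops stand, but each depends on individual or committee judgement and none sets the restart condition found in Table 16-4.

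Two further cautions stand. The action cell for the symptomatic row is empty in the extracted text, so the interruption and restart instruction is assigned to it by reading one merged cell. And 'severe' could qualify the whole symptom list, in which case mild nausea would not force a stop either. The contrast would then narrow to severe nausea or vomiting, and rash with eosinophilia would still be missing.

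Section 1.1 also reports no increased hepatic or hypersensitivity risk with inclisiran in earlier studies. That bears on how often the rule would be used, and does not explain the mismatch.

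**Conclusion.** The mismatch holds on the current text and is minor. A protocol-defined liver event is met either by an instruction to continue treatment or by discretion, while nausea or vomiting at the same enzyme level requires interruption and restricts restart. Table 16-4 permits restart under conditions; it does not require it.

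The conclusion assumes the merged action cell, 'severe' qualifying fatigue only, and the specific restart condition in Table 16-4 taking precedence over the general restart sentence in Section 6.5.1. It concerns participants with normal baseline tests, normal bilirubin and INR not above 1.5.

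The documents give no rate for this event, so the number affected cannot be computed; it is likely to be small. At most two of a participant's three injections are at issue.

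A reader might also infer a threat to the efficacy result. The documents do not support this: treatment discontinuations are handled by the treatment policy strategy (Protocol Section 2.1), and the notable liver criteria in SAP Table 5.3-2 are laboratory thresholds that do not depend on Table 16-4.

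**What to change.** At the next amendment, add rash with eosinophilia to the symptomatic row of Table 16-4, restricted to participants with normal ALT, AST and total bilirubin at baseline. The restriction is needed because that row also has an elevated-baseline cell, and Table 16-3 sets no symptom trigger for those participants. Keep the graded wording for fatigue and abdominal pain, and do not turn the whole Table 16-3 list into a mandatory stop. A note sending malaise, non-severe fatigue and other abdominal pain to Section 10.2.1 would be a useful but optional clarification.

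No new assay is needed: Table 8-3 already includes "Differential (% of Basophils, Eosinophils, Lymphocytes, Monocytes, Neutrophils" in hematology. The cost is one table entry and a rare extra dose hold at Day 90 or Day 270, permanent if no other etiology is found. A hold at Day 90 would remove the second of the two injections given before the Day 180 endpoint; the participant would remain in the primary analysis.

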16.5 Appendix 5: Sampson Criteria for Diagnosing Anaphylaxis

Anaphylaxis is highly likely when any one of the following three criteria is fulfilled:

1. Acute onset of an illness (minutes to several hours) with involvement of the skin, mucosal tissue, or both (eg, generalized hives, pruritus or flushing, swollen lips-tongue-uvula)

AND AT LEAST ONE OF THE FOLLOWING:

- a. Respiratory compromise (eg, dyspnea, wheeze-bronchospasm, stridor, reduced peak expiratory flow [PEF], hypoxemia)
- b. Reduced blood pressure or associated symptoms of end-organ dysfunction (eg, hypotonia [collapse], syncope, incontinence)

2. Two or more of the following that occur rapidly after exposure to a likely allergen for that patient (minutes to several hours):

- a. Involvement of the skin-mucosal tissue (eg, generalized hives, itch-flush, swollen lips-tongue-uvula)
- b. Respiratory compromise (eg, dyspnea, wheeze, bronchospasm, stridor, reduced PEF, hypoxemia)
- c. Reduced BP or associated symptoms (eg, hypotonia [collapse], syncope, incontinence)
- d. Persistent gastrointestinal symptoms (eg, painful abdominal cramps, vomiting)

3. Reduced blood pressure after exposure to a known allergen for that patient (minutes to several hours):

- a. Infants and children: low systolic blood pressure (age specific) or $> 30\%$ decrease in systolic blood pressure*
- b. Adults: systolic blood pressure < 90 mmHg or $> 30\%$ decrease from that person's baseline

*Low systolic blood pressure for children is age specific and defined as: < 70 mmHg for age 1 month to 1 year; < 70 mmHg + [2 x age] for age 1 to years; < 90 mmHg for age 11 to 17 years.

Source: *Sampson et al 2005 and Sampson et al 2006*

16.6 Appendix 6: Recommended Neurological Examination

MOTOR FUNCTION

When assessing motor function, from a neurological perspective, the assessment should focus on arm and leg movement. You should consider the following:

1. Muscle size

2. Muscle tone
3. Muscle strength
4. Involuntary movements
5. Posture, gait

Symmetry is the most important consideration when identifying focal findings. Compare one side of the body to the other when performing your assessment.

Limb assessment of a conscious patient usually involves a grading of strength.

Table 16-7 Grade Strength

Grade strength	Description
5	Full range of motion against gravity and resistance; normal muscle strength
4	Full range of motion against gravity and a moderate amount of resistance; slight weakness
3	Full range of motion against gravity only, moderate muscle weakness
2	Full range of motion when gravity is eliminated, severe weakness
1	A weak muscle contraction is palpated, but no movement is noted, very severe weakness
0	Complete paralysis

NB: In a conscious patient, the single best test to quickly identify motor weakness is the “drift test”. Have the patient hold their arms outward at 90 degrees from the body. With palms up, have the patient close their eyes and hold the arms for a couple of minutes. “Drifting” will occur if one side is weak.

Lower Extremities

Assess the patient in a supine position. Ask him/her to separate both legs to test for hip abduction. Then ask the patient to bring the legs back together to test for hip adduction. Sit the patient on the side of the bed to assess knee flexion and extension. Ask the patient to flex and extend the knee. If able to do this, apply resistance as these movements are repeated. Test plantar and dorsiflexion by having the patient push down against your hand with their foot and then pull up against your hand with their foot. Remember to compare the left side to the right side.

Upper Extremities

Assess ability to flex elbow (biceps) and straighten (triceps). Assess ability to raise shoulders and return to a resting position. Assess wrist flexion and extension. Test each function with resistance. For focused upper extremity assessment, assess each digit for flexion, extension and lateral movement.

SENSORY FUNCTION

When assessing sensory function remember that there are three main pathways for sensation, and they should be compared bilaterally:

1. Pain and temperature sensation.
2. Position sense (proprioception).
3. Light touch.

Pain can be assessed using a sterile pin. Light touch can be assessed with a cotton wisp. To test proprioception, grasp the patient's index finger from the middle joint and move it side to side and up and down. Have the patient identify the direction of movement. Repeat this using the great toe.

Sensory Tests:

A number of tests for lesions of the sensory cortex can be done. Examples include the following:

- **Stereognosis:** The ability to recognize an object by feel. Place a common object in the persons hand and ask them to identify the object.
- **Graphesthesia:** "Draw" a number in the palm of the person's hand and ask them to identify the number.
- **Two-Point Discrimination:** Simultaneously apply two pin pricks to the skin surface. Continually repeat the test while bringing the two pins closer together, until the individual can no longer identify two separate stimuli. The finger tips are the most sensitive location for recognizing two point differences while the upper arms, thighs and back are the least sensitive.
- **Extinction:** Touch the same spot on both sides of the body at the same time (eg, the left and right forearms. Ask the individual to describe how many spots are being touched. Normally, both sides are felt; with sensory lesions the individual will sense only one.
- **Point Locations:** Touch the surface of the skin and remove the stimulus quickly. Ask the individual to touch the spot where the sensation was felt. Sensory lesions can impair accurate identification, even if they retain their sensation of light touch.

TONE and REFLEXES

Upper motor neuron problems (brain and spinal cord) are associated with increased tone. Lower motor neuron problems are associated with decreased tone.

Look at the muscles on each side of the body in pairs. Assess for symmetry of bulk.

Evaluation of the stretch reflexes assesses the intactness of the spinal reflex arc at various spinal cord levels. The limb should be relaxed while applying a short and snappy blow with a reflex hammer. Hold the hammer loosely in a relaxed manner, making a wrist action. Allow the hammer to bounce.

Table 16-8 Reflex responses

Reflex responses	Description
0	No response
1+	Diminished, low normal
2+	Average, normal
3+	Brisker than normal
4+	Very brisk, hyperactive

Lower motor neuron disease is associated with 0 or 1+, upper motor neuron disease is associated with 3+ or 4+.

Biceps Reflex (C5 – C6)

Support the forearm on the examiners forearm. Place your thumb on the bicep tendon (located in the front of the bend of the elbow; midline to the anticubital fossa). Tap on your thumb to stimulate a response.

Triceps Reflex (C7-C8)

Have the individual bend their elbow while pointing their arm downward at 90 degrees. Support the upper arm so that the arm hangs loosely and “goes dead”. Tap on the triceps tendon located just above the elbow bend (funny bone).

Brachioradialis Reflex (C5-C6):

Hold the person’s thumb so that the forearm relaxes. Strike the forearm about 2-3 cm above the radial styloid process (located along the thumb side of the wrist, about 2-3 cm above the round bone at the bend of the wrist). Normally, the forearm will flex and supinate.

Quadriceps Reflex (Knee jerk) L2 – L4

Allow the lower legs to dangle freely. Place one hand on the quadriceps. Strike just below the knee cap. The lower leg normally will extend and the quadriceps will contract.

If the patient is supine: Stand on one side of the bed. Place the examiners forearm under the thigh closest to the examiner, lifting the leg up. Reach under the thigh and place the hand on the thigh of the opposite leg, just above the knee cap. Tap the knee closest to the examiner, (the one that has been lifted up with the examiners forearm).

Achilles Reflex (ankle jerks) L5 – S2:

Flex the knee and externally rotate the hip. Dorsiflex the foot and strike the Achilles tendon of the heel. In conscious patients, kneeling on a chair can help to relax the foot.

Heel Lift

While the patient is supine, bend the knee and support the leg under the thigh. Have the leg “go dead”. Briskly jerk the leg to lift the heel of the bed. Normally, the leg will remain relaxed and the heel will slide upward; increased tone will cause the heel and leg to stiffen and lift off the bed.

Babinski Response:

Dorsiflexion of the great toe with fanning of remaining toes is a positive Babinski response. This indicates upper motor neuron disease. It is normal in infants.

CEREBELLAR FUNCTION

The cerebellum is responsible for muscle coordination and balance on the same side. To test cerebellar function use the following tests:

1. Finger to finger test: have the patient touch their index finger to your index finger (repeat several times).
2. Finger to nose test: perform with eyes open and then eyes closed.
3. Tandem walking: heel to toe on a straight line.
4. Romberg test: stand with feet together and arms at their sides. Have patient close his/her eyes and maintain this position for 10 seconds. If the patient begins to sway, have them

open their eyes. If swaying continues, the test is “positive” or suggestive of cerebellum problems.

Dizziness that occurs in response to position changes is usually blood pressure initiated. If the patient sways during a Romberg test, but stops when the eyes are opened, the problem is probably visual or CN VIII (vestibular).
